**Phase B) Pilot RCT**

Inclusion criteria: lactating women of at least 18 years of age and their exclusively breastfed infants within 30 days of delivery with informed consent. Children 6-59 months who are orally feeding with caregiver informed consent.

Exclusion criteria: regular maternal consumption of moringa in the month prior to study enrollment, receipt and consumption of food supplementation program, or inability to feed orally; for infant, significant congenital disease, inability to feed orally. For child: inability to feed orally or refusal to eat porridge (>3 days consecutively).

We anticipate enrolling up to 50 mother-infant dyads in each of two arms and 50 children in each of two arms.

We propose starting enrollment as soon as all ethical approvals obtained, personnel hired, and study supplies obtained; there is no additional sample composition of subjects. This study targets women and infants as breastfeeding infants have the potential to receive the greatest benefit from moringa leaf supplementation to their lactating mothers.

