### We will implement:

A) a short acceptability study of acceptability, adherence, and preference for moringa dried leaf consumption and placebo consumption in porridge. Selection will be from lactating women 18 years and over and children 6-59 months; subjects will come from our target region of Kisumu.

B) a pilot placebo-controlled RCT of mother-infant dyads and their children 6-59 months who present for first postnatal check to two high volume rural maternal and child health centers in Kisumu, Kenya.

Inclusion criteria: lactating women of at least 18 years of age and their exclusively breastfed infants within 30 days of delivery with informed consent. Children 6-59 months of age who are eating food.

Exclusion criteria: regular maternal consumption of moringa, receipt and consumption of food supplementation program, or inability to feed orally; for infant, significant congenital disease, inability to feed orally. For mother or child: inability to orally feed or complete refusal (>3 days) to eat moringa or placebo porridge.

Sample size: 100 infant-mother pairs in each arm (n=400 participants total). 100 children in each arm (n=200)

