### Data collection:

Monthly anthropometrics for mother, infant, and child. These include infant weight, length and maternal and child weight, height/length, and mid-upper arm circumference.

Enrollment and exit quantitative surveys including but not limited to Food Frequency Questionnaire from which we will calculate Dietary

Diversity Score.

Mother, infant and child finger or finger/ heel stick for hemoglobin and capillary blood collection at study enrollment and exit.

Mother, infant and child feces collection at study enrollment and exit.

Daily recording by parent in provided diary of daily moringa percent consumption, incidence of diarrhea, diagnosis by health professional of medical condition in mother, infant, or child.

Lactating Women:

24 hour volume of breastmilk at study enrollment and exit

Breastmilk sample collection (est. 5ml) at study enrollment and exit

We would like to complete one more anthropometric measurement (weight and length) of enrolled infants in the next few months; this is 8-12 months from study start.

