### Phase B)

Participants regularly receive postnatal appointments at their health center for routine child check with health center staff. During this visit, our trained study personnel will enroll the participants and separately perform anthropometrics (weight, height or length, mid upper-arm circumference), collect blood, fecal, and breastmilk sample, and distribute study supplies. At monthly visits (month 1, 2, exit visit at month 3), followup will occur at the participant's study site. At these visits, study staff will perform anthropometrics, review porridge and/or moringa consumed, review parental diary, distribute study supplies, and at end visit will again collect blood, fecal, and breastmilk samples as applicable. Compliance with porridge-moringa ratio will be assessed by review of parent recorded amount consumed in the diary and direct visualization of percentage of porridge and leaf powder remaining prior to distribution. This will occur via verbal recall for parents identifying as illiterate.

Biological samples of mothers, infants and children (blood by heel stick or finger stick and stool) will be collected by trained study personnel at the presenting health center on enrollment and exit (3 months). Hemoglobin will be assessed by Hemoccue® utilizing a capillary (heel or finger) stick with direct readout. Capillary blood by heel or finger stick will be transferred to special paper and dried appropriately to create Dried Blood Spots by a standardized process and/or stored in aliquot containers. Fecal collection will occur on the day of monthly presentation to the health center, or kits and instructions will be given to caregivers and the stool collected by study personnel in the participant's village. Hemoglobin will be recorded to the nearest 0.1 g/dL by Hemoccue®. Stool, breastmilk, and blood samples will be immediately chilled and transported to Kenya Medical Research Institute Lab (KEMRI) in Kisumu, processed, and stored at -80 degree C freezers until transport. Samples will then be shipped on dry ice to the University of Kentucky or to the contracted laboratory for analysis. Breastmilk will be transported to Eurofin Laboratories or the laboratory of analysis. Breastmilk volume will be performed at enrollment and exit by 24 hour breastmilk volume pumped by hand pump that we supply and measured with the milk subsequently fed to the infant.

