We would like to complete one more anthropometric measurement (weight and length) of enrolled infants in the next few months; this is 8-12 months from study start. This would entail calling previously consented participants, asking them to come to the sub-county hospital, ensuring they agree to and sign the modified informed consent, and performing length and weight in the same method as previously and recording this is Redcap as previously done. We would provide the reimbursement of 500 Kenyan shillings, ~5USD.

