Head circumference: A standard measuring tape will be extended from the broadest part of forehead to the broadest part of the back of the head for infants. A mean of three consecutive measurements will be recorded to the nearest 0.1cm.

Standardization: For infants and children, weight for age, weight for length/height, and length/height for age will be compared to WHO standard deviation tables or Z scores and assigned their Z score. Wasting is low weight for length/height; stunting is low length/height for age; underweight is low weight for age. These are all measures of undernutrition. Mild undernutrition is defined for any of those parameters as <-1 to and including <-2; moderate undernutrition is <-2 to and including -3; severe undernutrition is <-3. Infants or children with Severe Acute Malnutrition defined as severe wasting (weight or length for height <-3), and/or the presence of nutritional edema will be referred to the nearest nutritional rehabilitation center for treatment as per standard WHO protocol. For mothers, Body Mass Index will be calculated (weight / height squared in metric units) and MUAC recorded.

Quality Control: Participants will be consecutively measured by the same instruments. The study coordinator will perform monthly quality control assessing variance between measurers for all measurements in order to ensure consistent measurement. Retraining and observed measurement will occur for any inconsistencies. Patients who do not arrive for their monthly visits will be contacted to remind them if contact information is available, and then visited at home if unable to come to the health center.

Vitamin A: serum retinol binding protein will survey infant vitamin A levels as an efficient measure of vitamin A at the individual level.

(46,47) Other assays of vitamin A are more informative at the population level. Measurement of the systemic inflammatory marker CRP (C-reactive protein) will allow for assessment of Vitamin A with and without correction for inflammation.

Iron: low hemoglobin is a proxy of childhood iron deficiency utilized internationally by UNICEF in LMIC. Iron levels can be measured via their transporters and intermediate forms. Calculation of a transferrin receptor-ferritin index from ferritin and soluble transferrin receptor will lessen the impact of fluctuations in ferritin from inflammation.(48,49)

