## Statistical Analysis Plan – 58219

Statistical Analysis: Data analyses were performed using SPSS v28 (IBM Corp. 2021) with graphing via SPSS and Prism GraphPad (v9.5.1). Using an intention-to-treat approach, we performed univariate and multivariable analysis for primary and secondary outcomes as change from baseline per individual/group and between groups. We used Pearson's (for normally distributed data) or Spearman's (for non-normally distributed data) correlation to examine relationships between continuous variables, Pearson's chi square and Fisher's exact tests between categorical variables, and independent t-test or Mann-Whitney U test between binary and continuous variables as appropriate. Paired samples t-tests or Wilcoxon matched-paired sign-rank test were used for paired data. Continuous variables are presented here as mean with standard deviation (if normally distributed) as mean  $\pm$  SD or median with interquartile range (if not normally distributed) as median, IQR, while categorical variables are presented with counts and percentages. An alpha-level of 0.05 was used to determine significance. All enrolled participants who continued study activities through at least the first month were analyzed regardless of loss to follow up.

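### The analysis is called intention-to-treat but leaves out anyone who stopped within the first month, and no method for missing outcomes is given

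*Combined protocol and SAP*

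**What the plan says.** The Statistical Analysis Plan is one paragraph, written in the past tense. It states the principle: "Using an intention-to-treat approach, we performed univariate and multivariable analysis for primary and secondary outcomes as change from baseline". It closes with the analysed set: "All enrolled participants who continued study activities through at least the first month were analyzed regardless of loss to follow up".

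Three other places fix the timing. Under Intervention, mothers and children take moringa or placebo porridge daily for three months. Under Research Procedures, Phase B, the enrolment visit is where staff take anthropometry, "collect blood, fecal, and breastmilk sample, and distribute study supplies"; follow-up visits come at months 1, 2 and 3. Under Data collection, anthropometry is monthly, while blood, stool and breastmilk are taken only at enrolment and exit.

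The documents describe no analysis of all randomised participants, no handling of missing outcomes and no sensitivity analysis.

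**The concern.** Intention-to-treat keeps the groups that randomisation made. Here membership depends on something that happens after enrolment, during treatment. The phrase about loss to follow-up protects only people lost after month 1, and even for them the plan does not say how a missing month-3 value is treated.

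If those who leave early differ in growth or nutrition from those who stay, and do so differently in the two arms, the analysed groups are no longer comparable. Equal numbers leaving each arm would not settle the matter if different kinds of people leave. What is at stake is the between-arm comparison that Aim 2 sets out to test, at the plan's alpha of 0.05.

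**Working it through.** **Timing.** Month 1 is the first visit after enrolment and falls one third of the way through a three-month intervention. The condition therefore arises during treatment. I take allocation to occur by the enrolment visit, because supplies are handed out then; the documents do not state the moment.

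**Plan's own figure.** There is none for early exit or refusal, so nothing can be reproduced directly. The only allowance is in the justification of the number of children: 82 infants per arm required, 100 recruited, a margin of (100 − 82)/100 = 18%. It covers loss over the whole study together with a smaller effect. The 82 does not itself reproduce: 25% against 6.5%, two-sided 5%, 80% power, gives [1.96·√(2·0.1575·0.8425) + 0.842·√(0.25·0.75 + 0.065·0.935)]² / 0.185² = 60 per arm, or 71 with continuity correction. I use 18% only as a generous upper end.

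**Inputs from the documents.** 50 per arm for infants and for children (Study Population, Phase B); 100 per arm in Study Design; 25% stunting; planned difference 25 − 6.5 = 18.5 points, which is the infant effect at 3 months.

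**Bound with no assumption about leavers.** With x stunted among those seen and k of n unseen, the full-arm percentage lies between x/n and (x + k)/n, a width of k/n.
- 1 of 50: 2 points (1 of 100: 1 point)
- 5 of 50: 10 points
- 9 of 50: 18 points, about the planned difference

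**Illustration with no true effect.** Assumed, not from the documents: a share r = 5-18% leaves before month 1, with stunting s = 10-40% among leavers. Stunting shown in an arm = (0.25 − r·s)/(1 − r).
- r = 0.05: (0.25 − 0.020)/0.95 = 24.2%, or (0.25 − 0.005)/0.95 = 25.8%
- r = 0.10: (0.25 − 0.040)/0.90 = 23.3%, or (0.25 − 0.010)/0.90 = 26.7%
- r = 0.18: (0.25 − 0.072)/0.82 = 21.7%, or (0.25 − 0.018)/0.82 = 28.3%

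False difference between arms:
- same share and same kind leave both arms: 0
- one arm only: 0.8, 1.7 and 3.3 points
- same share in both, opposite kinds: 1.6, 3.3 and 6.6 points

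**Effect on the error rate.** Two-sided 5% is assumed, since sidedness is not stated. With δ = false difference / standard error, the rate is Φ(−1.96 + δ) + Φ(−1.96 − δ), using the reduced arm sizes.
- One arm, r = 0.18: standard error √(0.25·0.75/50 + 0.217·0.783/41) = 8.9 points, δ = 0.37, rate 6.6%. The smaller r give 5.1% and 5.4%.
- Opposite kinds, r = 0.18: standard error √((0.217·0.783 + 0.283·0.717)/41) = 9.5 points, δ = 0.69, rate 10.6%. The smaller r give 5.4% and 6.5%.

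**The case against.** The strongest reply is that the rule mostly means having one measurement after baseline. Outcomes are changes from baseline, month 1 is the first chance to observe a change, and the rule keeps everyone lost later. It is disclosed in the same paragraph as the label. All of that stands, and it is why the set is fairly called modified intention-to-treat. A reader might infer a per-protocol set, but the text contains no adherence condition. What does not follow is that early leavers must be dropped: their baseline is measured at enrolment, so a model or imputation can keep them.

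Second, few may leave. The Quality Control text says "Patients who do not arrive for their monthly visits will be contacted to remind them if contact information is available", followed by home visits. That is plausible, but no count is given.

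Third, this is a pilot and the illustration rests on assumed values; its worst case needs 18% lost in both arms with opposite kinds of leaver, which nothing in the documents suggests. For infants, dislike of the porridge could act only through the mother. This lowers the weight of the point without removing it.

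A stronger reading is tempting: that allocated people who refused porridge were removed. Study Design lists as an exclusion "For mother or child: inability to orally feed or complete refusal (>3 days) to eat moringa or placebo porridge", and with supplies given at enrolment and no run-in described, refusal of study porridge might be seen only afterwards. The documents do not establish this. Refusal appears only in eligibility lists. The Study Population version is narrower, "For child: inability to feed orally or refusal to eat porridge (>3 days consecutively", and can be checked by history before entry. No text says an allocated refuser is withdrawn or left out of the analysis. The planned diary, "Daily recording by parent in provided diary of daily moringa percent consumption", and the checks of leftover porridge fit following people who eat little. This is a matter for clarification.

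**Conclusion.** The point holds for the first-month condition. The label and the analysed set do not match, the condition arises during treatment, and nothing else in the plan compensates. Bias requires early exit that is related to outcome and differs between arms in number or kind; the documents neither show this nor rule it out.

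The direction is unknown, so a reader should not infer that the set favours moringa. The likely size is modest: up to 3.3 points (18% of the planned 18.5) if one arm alone loses people, and up to 6.6 points (36%) in the extreme case, all under the assumed exit and stunting ranges. It is worth correcting because the remedy is cheap, but it does not by itself discredit the pilot.

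**What to change.** In the Statistical Analysis Plan:

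1. Analyse all randomised participants in their allocated arm and state the missing-outcome method. For monthly anthropometry, a repeated-measures model with baseline as one of the outcomes keeps people who have only a baseline value. For blood, stool and breastmilk, measured only at enrolment and exit, use multiple imputation.
2. Report by arm the numbers randomised, leaving before month 1, and analysed.
3. Keep the first-month set as a sensitivity analysis labelled modified intention-to-treat.

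As a secondary clarification, state that the Study Design refusal criterion applies before allocation, and that any allocated participant who refused porridge stays in the analysis, with refusal reported by arm as adherence.

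The later infant measurement ("This would entail calling previously consented participants, asking them to come to the sub-county hospital") should not stand in for the month-3 outcome: it covers infants only, falls 8-12 months from study start and needs a modified consent.

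The cost is wording, one table and one re-run, with no new participants or measurements. The downside is that people with only baseline data add little information and the result leans partly on an untestable missing-data assumption. Showing both sets side by side lets the reader judge how much that matters.
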